20. Unresectable Stage III or Stage IV melanoma, as per American Joint Committee on Cancer staging system not amenable to local therapy.
21. Documentation of V600-activating BRAF mutation status or consent to BRAF.
22. V600 mutation testing during the screening period.
23. Must not have ocular melanoma.

Subjects with urothelial carcinoma:

24. Histologically or cytologically confirmed urothelial carcinoma of the renal pelvis, ureter, urinary bladder, or urethra that is transitional cell or mixed transitional/nontransitional (predominantly transitional) cell type.
25. Stage IV locally advanced or metastatic urothelial carcinoma (according to American Joint Committee on Cancer 7th edition guidelines) with documented disease progression while on a PD-1 pathway-targeted therapy. Progression following cessation of PD-1 pathway-targeted therapy is not sufficient.

3-2- Subject Exclusion Criteria

A subject who meets any of the following criteria will be excluded from the study:

1. Laboratory and medical history parameters not within Protocol-defined range. Cycle 1 Day 1 laboratory assessments for the determination of eligibility do not need to be performed if the screening labs were performed within 7 days of Cycle 1 Day 1. If the screening lab assessments were performed more than 7 days before Cycle 1 Day 1, the hematology, serum chemistry, and liver chemistry lab results must be confirmed on Cycle 1 Day 1 before treatment initiation.
 - a. Absolute neutrophil count $< 1.5 \times 10^9/L$.
 - b. Platelet count $< 100 \times 10^9/L$.
 - c. Hemoglobin < 8 g/dL (transfusion is acceptable to meet this criterion).

- d. Serum creatinine $\leq 1.5 \times$ institutional upper limit of normal (ULN) OR measured or calculated creatinine clearance (glomerular filtration rate can also be used in place of creatinine or CrCl) $< 50 \text{ mL/min}$ for subjects with creatinine levels $> 1.5 \times$ institutional ULN).
 - e. Aspartate aminotransferase, ALT, and alkaline phosphatase $\leq 2.5 \times$ ULN.
Note: Subjects with 1) bone metastases and 2) no hepatic parenchymal metastases on screening radiographic examinations may enroll if the alkaline phosphatase is $< 5 \times$ ULN. Subjects with 1) bone metastases and 2) hepatic parenchymal metastases on screening radiographic examinations may enroll if the alkaline phosphatase is $< 5 \times$ ULN only with medical monitor approval.

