4.1.2.1.2. Treatment Group A Treatment Sequencing Tumor Biopsy Cohorts (Part 2)

The sequencing biopsy cohorts require 3 tumor biopsies to identify epigenetic changes and changes in the tumor microenvironment induced by each of the components of the regimen. All subjects will have tumor biopsies at baseline and 2 additional biopsies while on study treatment.

Approximately 25 subjects will be enrolled in Expansion Cohorts A-3 and A-4, and approximately 10 subjects will be enrolled in Expansion Cohort A-5. The eligible tumor types for Expansion Cohorts A-3, A-4, and A-5 are HNSCC, melanoma, urothelial carcinoma, and MSS CRC. In Expansion Cohorts A-3 and A-4, subjects with tumor types other than MSS CRC must have had disease progression on a prior PD-1 pathway-targeted agent.

Five to 8 evaluable subjects per tumor type in Expansion Cohorts A-3 and A-4, and 10 subjects in Expansion Cohort A-5 will initiate treatment and have tumor biopsies performed as indicated in Table 5.

Table 5: Treatment Group A Treatment Sequencing Tumor Biopsy Cohorts (Part 2)

Cohort	Treatment Sequence	Biopsy Sequence	Tumor Type (n)
Expansion Cohort A-3	Azacitidine monotherapy during Week -1 (5 doses), initiate pembrolizumab and epacadostat on C1D1 (window + 5 days from the date of the fifth azacitidine dose; should begin after biopsy #2), 5 doses of azacitidine will be administered in Cycles 2 and 3.	Biopsy #1 at baseline. Biopsy #2 on C1D1 (window Day -5 to C1D1, biopsy before pembrolizumab/epacadostat administration). Biopsy #3 during Week 5 or 6.	HNSCC (5-8) Melanoma (5-8) Urothelial carcinoma (5-8) MSS CRC (5-8)
Expansion Cohort A-4	Pembrolizumab and epacadostat for 1 cycle, initiate azacitidine after biopsy #2, 5 doses of azacitidine will be administered in Cycles 2 and 3.	Biopsy #1 at baseline. Biopsy #2 on C2D1 (window C1D15 to C2D1, biopsy before azacitidine administration). Biopsy #3 during Week 8 or 9.	HNSCC (5-8) Melanoma (5-8) Urothelial carcinoma (5-8) MSS CRC (5-8)
Expansion Cohort A-5	Pembrolizumab monotherapy for 1 cycle, initiate epacadostat and azacitidine after biopsy #2, 5 doses of azacitidine will be administered in Cycles 2 and 3.	Biopsy #1 at baseline. Biopsy #2 on C2D1 (window C1D15 to C2D1, biopsy before epacadostat/azacitidine administration). Biopsy #3 during Week 8 or 9.	First-line melanoma (10)

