Evaluation Window	Day -28 to Day -1	CID1-7 days	D1	± 3 d	DS-7	±3 d	+Sd	EOT + 42-49 d	
ADMINISTRATIVE PROCEDURES									
Informed consent	X								
ContactIRT	X	X	X	X		X	X		
Inclusion/exclusion criteria	X	X							
Medical and cancer history	X								
Prior/concomitant medications	X	X*	X	X	X*	X	X	X	* To be assessed at baseline before first azacitidine dose and on the fifth day of azacitidine dose administration.
Distribute reminder cards	X	X	X	X	X	X	X		
Study drug dispensing			X	X		X			
Assess study drug compliance				X		X	X		
CLINICAL PROCEDURES AND ASSESSMENTS									
Physical examination/body weight and height*	X	X**	X	X	X**	X	X	X	* Comprehensive examination at screening, targeted physical examination thereafter. Height at screening only. ** To be assessed at baseline before first azacitidine dose and on the fifth day of azacitidine dose administration.
Vital signs	X	X*	X	X	X**	X	X	X	* To be assessed at baseline before first azacitidine dose and on the fifth day of azacitidine dose administration. **Visit to occur on the fifth day of azacitidine dose administration.

Table 31: Schedule of Assessments (Treatment Group A: Part 2 Expansion Cohort A-3, Azacitidine Monotherapy Lead-In) (Continued)

Visit Day	Screening	Treatment					EOT	Safety Follow-Up	Notes
		Week-1	C1 D1	C2 D1	C2 DS-7	C3+ D1			
Evaluation Window	Day -28 to Day -1	CID1-7 days	D1	± 3 d	DS-7	±3 d	+S d	EOT + 42-49 d	
ECOG performance status	X	X*	X	X	X**	X	X	X	* To be assessed at baseline before first azacitidine dose and on the fifth day of azacitidine dose administration. **Visit to occur on the fifth day of azacitidine dose administration.
12-lead ECG	X*		X**	X**		X***,1'	X''	X''	* Triplicate ECG at baseline. ** Timed triplicate ECGs (separated by 5 min ± 2 min) at predose and at 2 and 4 hours(± 15 min) postdose. *** ECG will be performed on DI of every other cycle after C2 (eg, C4, C6, and C8). '' ECGs only need to be performed in triplicate if there has been a QT prolongation on study or the ECG shows a clinically significant abnormality not present at baseline.
AE assessment	X	X*	X	X	X*	X	X	X	* To be assessed at baseline before first azacitidine dose and on the fifth day of azacitidine dose administration.
Laboratory assessments	X	X*	X	X	X*	X	X	X	* Visit to occur on the fifth day of azacitidine dose administration.
TUMOR BIOPSY COLLECTION									

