Tumor biopsy/ tissue collection	X		X*			X**			* A second mandatory on-treatment biopsy will be collected prior to CID1 (window Day -5 to predose on CID1). **A third mandatory on-treatment biopsy will be collected during Week 5 or 6. Additional biopsies may be collected once the subject meets the requirements for SD, response, or progression by radiographic disease assessment. Detailed instructions for tissue collection, processing, and storage can be found in the study procedures manual. Fine needle aspirates are not acceptable.

Table 31: Schedule of Assessments (Treatment Group A: Part 2 Expansion Cohort A-3, Azacitidine Monotherapy Lead-In) (Continued)

Visit Day	Screening	Treatment					EOT	Safety Follow-Up	Notes
		Week -1	C1 D1	C2 D1	C2 D5-7	C3+ D1			
Evaluation Window	Day -28 to Day -1	C1D1-7 days	D1	± 3d	D5-7	±3 d	+ 5 d	EOT + 42-49 d	
STUDY DRUG ADMINISTRATION									
Administer azacitidine in clinic		X*		X**	X**	X**			* Five doses of azacitidine will be administered in the clinic over a 5- to 7-day period in Week -1 (before C1D1 of pembroliztunab/epacadostat). ** Azacitidine administration should continue with 5 doses administered in the clinic on D1-D7 of Cycles 2 and 3. Subjects who remain on treatment beyond the Week 9 scan should continue to receive azacitidine until the second on-study scan (up to the Week 18 scan, for a maximum of 3 additional cycles).
Administer epacadostat in clinic*			X**	X					* Subjects should withhold their AM dose of epacadostat on days. It should be administered in the clinic following the trough collection on C1D1 and C2D1. ** C1D1 treatment should be initiated within a + 5 day window from the date of the fifth azacitidine dose.
Administer pembroliztunab in clinic			X*	X		X			* C1D1 treatment should be initiated within a + 5 day window from the date of the fifth azacitidine dose.
EFFICACY ASSESSMENTS									
Radiologic tumor assessments*	X					X	X		* Every 9 weeks (63 ± 7 days) until disease progression. After 12 months of study treatment, imaging frequency may be reduced to every 12 weeks. Imaging should not be delayed for delays in cycle starts or extension of combination treatment cycle intervals.

Table 32: Laboratory Assessments (Treatment Group A: Part 2 Expansion Cohort A-3, Azacitidine Monotherapy Lead-In)

Laboratory Assessment Window	Screening	Week -1	Treatment				EOT	Safety	Notes
			C1	C2	C2	C3+			
			DI	DI	DS-7	DI			
	Day -28 to Day -1	C1D1 - 7 days	DI	±3 d	DS-7	±3 d	+Sd	EOT+ 42-49 d	

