Laboratory Assessment Window	Day -28 to Day -1	D1	Treatment										EOT + 42-49 d	* For subjects receiving INCB059872 QoD, an additional visit is required during C2 on D2 or D4 so that the samples are collected on the day when INCB059872 is administered.	
			± 3 d	± 3 d	± 3 d	D2 or D4	± 3 d	± 3 d	± 3 d	± 3 d	± 3 d	+ 5 d			

Table 49: Local Laboratory Tests: Required Analytes

Serum Chemistries	Hematology	Urinalysis With Microscopic Examination	Hepatitis Screening	Coagulation
Albumin Alkaline phosphatase ALT AST Bicarbonate Blood urea nitrogen Calcium Chloride Creatinine Glucose Lactate dehydrogenase Phosphate Potassium Sodium Total bilirubin Direct bilirubin (if total bilirubin is elevated above ULN) Total protein Uric acid	Complete blood count, including: Hemoglobin Hematocrit Platelet count Red blood cell count White blood cell count Differential count, including: Basophils Eosinophils Lymphocytes Monocytes Neutrophils Absolute values must be provided for: WBC differential laboratory results: Lymphocytes Neutrophils	Color and appearance pH and specific gravity Bilirubin Glucose Ketones Leukocytes Nitrite Occult blood Protein Urobilinogen	HBV surface antigen HBV-DNA HCV antibody HCV-RNA	PT PTT INR
		Endocrine Monitoring		Pregnancy Testing
		ACTH HbA1c Semi quantitative Prolactin TSH Free thyroxine (T4) Total triiodothyronine (T3) Semi quantitative testosterone		Women of childbearing potential only require a semi quantitative test at screening (must be performed within 72 hours before the first dose of study drug) and at safety follow-up. Pregnancy tests (semi quantitative or urine) should be repeated if required by local regulations.

ACTH = adrenocorticotropic hormone.

Note: Additional tests may be required, as agreed by investigator and sponsor, based on emerging safety data.

6-L Screening

Screening is the interval between signing the ICF and the day the subject is enrolled in the study (Cycle 1 Day 1 or Day 1 of Week -1 for Expansion Cohort A-3). Screening may not exceed 28 days. Assessments that are required to demonstrate eligibility may be performed over the course of 1 or more days during the screening process.

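### For Cohort A-3, the eligibility laboratory re-check is tied to Cycle 1 Day 1, after azacitidine has begun, and the schedule tables do not clearly require a draw before the first dose

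*Protocol*

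**What the plan says.** Exclusion 1 in Protocol section 3.2, repeated in the synopsis, covers every cohort. Cycle 1 Day 1 eligibility tests "do not need to be performed if the screening labs were performed within 7 days of Cycle 1 Day 1". Otherwise "the hematology, serum chemistry, and liver chemistry lab results must be confirmed on Cycle 1 Day 1 before treatment initiation". There is no A-3 provision.

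In A-3 the first study drug is not given on Cycle 1 Day 1. Table 5 in section 4.1.2.1.2 gives the sequence as "Azacitidine monotherapy during Week -1 (5 doses), initiate pembrolizumab and epacadostat on C1D1". Table 31 adds "Five doses of azacitidine will be administered in the clinic over a 5- to 7-day period in Week -1" and "C1D1 treatment should be initiated within a + 5 day window from the date of the fifth azacitidine dose".

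Other passages do adapt to this cohort. Section 6.1 ends screening on "the day the subject is enrolled in the study (Cycle 1 Day 1 or Day 1 of Week -1 for Expansion Cohort A-3"), with a cap of 28 days, and section 6.2 makes the same substitution when it limits the time from consent. Section 6.1 also has screening results reviewed for eligibility before enrollment or dosing. However, it accepts routine-care results obtained before consent if they fall within 28 days of Cycle 1 Day 1, with no A-3 variant.

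The schedules are mixed. Table 31 marks the inclusion/exclusion check at Screening and Week -1, not at Cycle 1 Day 1. Its laboratory row carries the note "Visit to occur on the fifth day of azacitidine dose administration". The Week -1 entries for medications, physical examination, vital signs, ECOG status and adverse events call for an assessment ahead of the first azacitidine dose as well as on the fifth day. Table 32 marks chemistry and hematology at Week -1 with no timing note.

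**The concern.** The 7-day rule is there so that nobody starts study drug on out-of-date laboratory results. In A-3 the rule protects the start of pembrolizumab and epacadostat but not the start of azacitidine, which comes first. A re-check on Cycle 1 Day 1 cannot precede the first study drug.

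Two things are at stake. First, azacitidine could be started on results older than the protocol otherwise accepts. Second, neutrophil, platelet and hemoglobin limits (criteria 1a to 1c) could be applied to blood drawn after a drug that section 1.8.3 associates with neutropenia, thrombocytopenia and anemia. A subject who was eligible before dosing could then meet an exclusion criterion because of study drug, in a protocol that does not allow eligibility deviations (section 3).

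There is a smaller analysis consequence. SAP section 4.2.3 defines baseline as the last value before any study drug. Without a pre-dose Week -1 draw, the A-3 laboratory baseline is the screening value, whatever its age.

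**Working it through.** No sample size, power or error rate is involved. The check is a day count, followed by a comparison of the passages.

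**Inputs**
- Five azacitidine doses over 5 to 7 days (Table 31). With the first dose on day 0, the fifth falls on day 4 to day 6.
- Cycle 1 Day 1 falls 0 to 5 days after the fifth dose (Table 31).
- The re-check is waived if screening tests fall within 7 days of Cycle 1 Day 1 (exclusion 1).
- Screening lasts at most 28 days (section 6.1).

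**Step 1: lag from first azacitidine to Cycle 1 Day 1**
- Shortest: 4 + 0 = 4 days.
- Longest: 6 + 5 = 11 days.
- Nominal, from the Week -1 column heading in Table 31: 7 days.

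The 4-day figure assumes Cycle 1 Day 1 may fall on the day of the fifth dose. If it must be the next day or later, the shortest lag is 5 days.

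**Step 2: when the re-check is triggered**
Let s be the age in days of the screening tests at first azacitidine. The re-check applies when s + lag > 7.
- Lag 4: triggered for s from 4 to 28; tests 1 to 3 days old are exempt.
- Lag 7 or more: triggered for every s from 1 to 28, since 1 + 7 = 8 > 7.

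At the nominal lag, any screening test taken at least a day before azacitidine triggers the re-check, and the re-check always falls after azacitidine.

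**Step 3: oldest results at first azacitidine, if no pre-dose draw is taken**
- Screening counted to Day 1 of Week -1 (section 6.1): 28 days.
- Counted back from Cycle 1 Day 1 instead: 28 − 11 = 17 to 28 − 4 = 24 days; 28 − 7 = 21 at the nominal lag.

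Each figure exceeds 7 days.

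**Step 4: where the passages place the A-3 check**

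| Passage | Timing for A-3 |
|---|---|
| Exclusion 1 | Cycle 1 Day 1, after five azacitidine doses |
| Sections 6.1 and 6.2 | Enrollment at Day 1 of Week -1 |
| Table 31, inclusion/exclusion row | Screening and Week -1 |
| Table 31, laboratory row | Fifth azacitidine day |
| Table 31, neighbouring Week -1 rows | Before first azacitidine and fifth day |
| Table 32, chemistry and hematology | Week -1, no timing |

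No passage clearly requires a laboratory draw within 7 days before the first azacitidine dose. Table 32 permits one but does not ask for it.

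**The case against.** The strongest reply is that the A-3 schedule has already moved the eligibility decision to the lead-in. Table 29, for A-1 and A-2, marks the inclusion/exclusion check at Screening and Cycle 1 Day 1; Table 31 marks it at Screening and Week -1. Sections 6.1 and 6.2 set the A-3 start at Day 1 of Week -1, and section 6.1 wants eligibility confirmed before enrollment or dosing. In Table 32 the Week -1 chemistry and hematology draw lacks the fifth-day note found on the corresponding rows of Tables 30, 34 and 36, so a site may take it before dosing. All of this stands, and it narrows the point. It does not remove it: exclusion 1 and the Table 31 laboratory footnote still say something different.

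It can also be said that treatment initiation in exclusion 1 means the start of the doublet. The rule could then be met on Cycle 1 Day 1, but it would leave the first azacitidine dose uncovered.

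A reader might infer more than the documents support:
- **That every A-3 subject is affected.** The roughly 25 subjects are a planned number. Stale results arise only where screening tests were more than 7 days old at first azacitidine and no pre-dose Week -1 draw was taken.
- **That retained subjects are selected on marrow tolerance.** No cytopenia rate is given for the 4 to 11 days after starting this regimen. Section 1.7.2 expects the dose to limit hematologic toxicity, and section 1.8.6 reports no dose-limiting toxicities in Part 1.
- **That a subject failing on Cycle 1 Day 1 is denied the doublet.** This needs exclusion 1 to be read literally against the Table 31 check at Week -1.

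**Conclusion.** The inconsistency is real and confined to A-3. Exclusion 1 was not adapted to a cohort whose first study drug precedes Cycle 1 Day 1 by 4 to 11 days, and Tables 31 and 32 do not settle when the Week -1 laboratory draw is taken. A site following exclusion 1 and the Table 31 footnote could start azacitidine on screening results more than 7 days old: up to 28 days on the section 6.1 anchor, or 17 to 24 days if the window is counted from Cycle 1 Day 1. It could also apply eligibility limits to results obtained after azacitidine.

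This is a matter of eligibility and safety timing. It changes no endpoint, sample size or error rate. The documents do not give the number of A-3 subjects exposed. Amendment 4 records the decision to stop further enrollment, and SAP sections 4.1 and 5.2 confirm the early stop, so the practical effect is limited to A-3 subjects already enrolled.

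**What to change.** Reconcile exclusion 1 (section 3.2 and synopsis), the routine-care window in section 6.1 that counts 28 days from Cycle 1 Day 1, and Tables 31 and 32 for A-3. The anchor that sections 6.1 and 6.2 already use for this cohort, Day 1 of Week -1, is available for this. Give the Table 31 Week -1 laboratory row the timing its neighbouring rows carry (before the first azacitidine dose and on the fifth day), and make Table 32 match.

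Two related questions are for the sponsor, and this review does not choose either rule: whether the A-3 Cycle 1 Day 1 results bear on eligibility at all, and whether the Cycle 1 Day 1 anchor in exclusion 3 (resolution of earlier immune-related events) is intended for A-3.

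For subjects already enrolled, the study report can list the age of the qualifying laboratory results at first azacitidine and any subject judged ineligible on Cycle 1 Day 1 results.

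The cost is protocol wording, plus at most one routine local draw at a visit that already takes place.

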4.1.1. Dose-Escalation Phase (All Treatment Groups)

A 3 + 3 + 3 design will be used to assess the MTD, maximum tested dose, or PAD of the triplet combination of azacitidine, INCB057643, or INCB059872 with pembrolizumab and epacadostat in 21-day treatment cycles. The MTD will be defined as the highest dose at which less than one-third of the subjects (with a minimum of 6 subjects) have a DLT. When the MTD, maximum tested dose, or PAD has been determined or reached, the dose will be recommended for Part 2. The Part 2 expansion will begin after the determination of the MTD, maximum tested dose, or PAD; however, enrollment priority will be given to the open Part 1 dose-escalation cohort.

A minimum of 3 subjects will initially be enrolled in Cohort 1, and each subject will be observed for 21 days from the start of triplet combination therapy before enrollment in the next cohort begins. The dose of azacitidine, INCB057643, or INCB059872 (or epacadostat) will be escalated if 0 of the first 3 evaluable subjects enrolled has a DLT. If 1 of 3 subjects in Cohort 1 has a DLT, the cohort will be expanded to 6 subjects. If 1 of 6 subjects in Cohort 1 has a DLT, a new cohort of 3 subjects will be treated at the next higher dose level (Cohort 2). If 2 of 6 subjects in Cohort 1 have a DLT, that cohort will be further expanded to a total of 9 subjects. If $\leq 2/9$ subjects have a DLT, 3 subjects will be treated at the next higher dose level. If $2/3$, $3/6$, or $3/9$ subjects have a DLT within a cohort, dose de-escalation will be required, and Cohorts -1 or -2 will be tested. The MTD is defined as the highest dose level at which $\leq 1/6$ or $\leq 2/9$ subjects experience a DLT.

Subjects must have received $\geq 75\%$ of planned doses of study drug during the 21-day DLT (Treatment Group A) or 42-day DLT (Treatment Groups Band C) observation period or have had a DLT to be evaluable for dose tolerability (Treatment Group A: azacitidine [4 doses], epacadostat [32 doses], and pembrolizumab [1 dose]; Treatment Group B: INCB057643 [32 doses], epacadostat [32 doses], and pembrolizumab [1 dose]; Treatment Group C: INCB059872 [QD dosing, 32 doses; QoD dosing, 16 doses], epacadostat [32 doses], and pembrolizumab [1 dose]).

It is recognized that certain toxicities due to the combination agent (eg, including but not limited to gastrointestinal toxicity, including diarrhea; renal insufficiency; high-grade laboratory abnormalities; and rash) may initially be clinically indistinguishable from toxicities due to immunotherapy. Epacadostat will be held for these toxicities, and as a result, subjects may not receive $\geq 75\%$ of the prescribed dose during Cycle 1. In these cases, the principal investigators and medical monitor may assess subjects who receive dose intensities somewhat below 75% for the determination of DLTs, and consider in the adjudication process the specific toxicity encountered, the likely cause of the toxicity, and dose intensity and tolerability beyond Cycle 1. Additional subjects will be enrolled in a cohort to achieve the minimum of 3 evaluable subjects if dropouts or dose interruptions/reductions occur that result in a subject being nonevaluable for DLTs.

During the study, dose interruptions and/or dose modifications may be implemented based on toxicity as described in Section 5.4. However, dose modifications should not be made during the DLT observation period without discussion with the medical monitor. Intrasubject dose escalation is not permitted.

